## 6.1 Selection of Study Population

Patients will be enrolled from the offices of community dermatologists across Canada treating patients with Psoriasis. The sample of physicians invited to participate in the study will be selected in a way that it is a random representative sample of the Canadian population and distribution of dermatologists.

All patients with psoriasis treated at the participating centers will be potentially eligible

to be included in the study. Those fulfilling the study inclusion and exclusion criteria will be invited to participate in the study by the site investigator or designee. Treatment will be according to the treating physician's judgment and routine care and must adhere to the product monograph and regional regulatory requirements. Use of medications for the management of psoriasis that is off—label or not in accordance with existing regulations will not be permitted. Prior to inclusion in the study all patients will be required to sign a written informed consent agreeing to allow use of their data in the study. Since this is not an interventional study and patients are treated as per routine care the purpose of the informed consent will be to allow the use of the data and contact of the patients by the study personnel as required. The study protocol, informed consent, questionnaires and participating physicians will be approved by a central or local independent ethics review board as required by regional or institutional regulations.

Changing the patient's treatment including initiation of treatment with adalimumab must be exclusively the treating physician's decision and must be reached prior to patient screening and enrollment and has to be entirely independent of the conduct of the study. The observational nature of the study dictates that all treatments used in the current study, including adalimumab, must be prescribed as per routine care and in accordance to the Canadian and provincial marketing authorization and criteria.

#### 6.1.1 Inclusion Criteria

The following inclusion criteria will be applied:

- i. Adult > 18 years old
- ii. Has provided written informed consent allowing the use of their data for the study and providing permission for contact by the study personnel.

- iii. Active moderate or severe Plaque PS according to the judgment of the treating physician.
- iv. The treating physician has decided to change the current treatment or add additional treatments for any reason including but not limited to inadequate response, intolerance, sub-optimal compliance or patient preference.

#### 6.1.2 Exclusion Criteria

The following exclusion criteria will be applied:

- i. Currently participating in another prospective study with similar objectives.
- ii. Patient cannot or will not sign informed consent.
- iii. Presence of other condition that, in the opinion of the treating physician, prohibits the patient from participating in the study or obscures the assessment of the treatment of Plaque PS.

#### 6.2 Number of Patients to be Enrolled

A total of 660 patients will be enrolled in the current study from the practices of 30-40 dermatologists. A maximum of 30 patients per site will be allowed. Recruitment will be over a 24 month period. In order to provide adequate power to assess the effect of different treatment modalities, it will be recommended that 50% of the patients from each site will be initiated on treatment with adalimumab.

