Finally, continuous monitoring of the safety of adalimumab is essential in order to assess whether the safety profile in a real – life setting is comparable to that expected on the basis of the data reported in controlled clinical trials and to ensure detection of any emerging signal.

The current study will address the above questions by conducting a prospective observational study of Canadian patients with moderate to severe psoriasis for whom change of current treatment is indicated. Patients will enter the cohort at the time that their treatment is changed and therefore patients treated with topical agents, traditional systemic agents and adalimumab will be eligible to be included in the study. The rationale for limiting the anti-TNF alpha agent to adalimumab is based on the prevention of within class variation with respect to clinical decision making, response to treatment and incidence of adverse events.

Follow up will be for 24 months and assessments will be as per routine clinical care and according to the judgment of the treating physician. However, follow up visits at approximately 3, 6, 12, 18 and 24 months will be recommended.

There will be a total of 660 patients with psoriasis enrolled from the clinics of 30 - 40 Canadian community dermatologists. The sample of clinicians will be a random proportional representation of the distribution of dermatologists and patients in Canada, thus allowing valid generalization to the Canadian population of psoriasis patients. In addition, enrollment of the patients in the study will be on the basis of change in current treatment due to lack of response or tolerability. The decision to change treatment must be reached prior to enrollment in and independently of the current study.

The study will assess clinical and patient reported outcomes that are relevant in the management of psoriasis and its impact on the patient's quality of life and societal burden

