## 6.5 Study Conduct

The following sections describe the details regarding the execution of the study.

This is a multi-center Canadian observational study utilizing a prospective cohort design. As an observational study there will be no interventions or interference with the routine care of the patient.

All treatments will be prescribed and utilized as per the judgment of the treating physician and in accordance with the product monograph and regional requirements.

As per the product monograph: "Before initiation, during and after treatment with adalimumab patients should be evaluated for active or latent tuberculosis infection with a

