## 6.5.1 Description of Activities

#### **Screening and Baseline Assessments:**

Participating physicians will be asked to assess for potential eligibility all sequential patients with Psoriasis for whom a change in treatment regimen is being considered.

Following an explanation of the study by the physician or designee, a written informed consent will be signed by the patients that agree to participate. Subsequent to obtaining written informed consent, potential eligible patients will be assessed for inclusion and exclusion criteria. Those that qualify will be entered in the study cohort. All baseline assessments will be conducted during the baseline / screening visit. The physicians or designee will be required to complete all data on the baseline visit section of the Case report Form using data ascertained by interview or examination of the patient or review of the patient's chart.

There are no laboratory examination requirements for the current study beyond those that are part of routine care. Historical data of up to six months could be used for the baseline values for laboratory tests.

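### Protocol 6.2 recommends a 50% adalimumab share at each site for power, which conflicts with the rule that starting adalimumab be decided independently of the study

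*Protocol*

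**What the plan says.** Protocol 6.2 sets the number of patients: "A total of 660 patients will be enrolled in the current study". It then gives a reason, "In order to provide adequate power to assess the effect of different treatment modalities", and a recommendation to sites: "it will be recommended that 50% of the patients from each site will be initiated on treatment with adalimumab".

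The text on how treatment is chosen reads differently:

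- Protocol 6.1: a change of treatment, including a start of adalimumab, "must be exclusively the treating physician's decision". It must come before screening and enrolment and "has to be entirely independent of the conduct of the study". SAP 2.9 repeats this.
- Protocol 4.0: "The decision to change treatment must be reached prior to enrollment in and independently of the current study".
- Protocol 6.5: "there will be no interventions or interference with the routine care of the patient".

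On who is assessed and entered:

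- Protocol 6.5.1 asks physicians to assess consecutive psoriasis patients "for whom a change in treatment regimen is being considered".
- Protocol 6.1 says that patients who meet the criteria will be invited.
- Inclusion criterion iv in Protocol 6.1.1 requires that the physician has already decided to change or add treatment.

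Protocol 10.3 calls the 1:1 ratio of adalimumab to the comparators expected. SAP 2.7 gives it as 2:1:1 (330:165:165). SAP 3.2 attributes allocation to the physician's judgment and does not mention a site share.

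**The concern.** The study asks how adalimumab compares with topical and traditional systemic agents in ordinary practice. That question depends on treatment being chosen as it would be without the study. A share recommended to each site by the study, and justified by power, is on its face study input to that choice.

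If the share affected prescribing, the comparison would no longer describe routine care. If it affected only who is entered, the cohorts would depend on a selection step that nobody records. The descriptive objectives (patient profile, practice patterns, burden of illness) and the generalisation to Canadian patients claimed in Protocol 4.0 would be exposed in either case.

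The plan also gives no means of checking. Table 1 and the CRF sections in Protocol 9.0 list no date for the treatment decision. The audit of all sites in Protocol 8.0 covers the inclusion and exclusion criteria, and these do not include independence of the choice of agent.

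**Working it through.** **The plan's own figure.** 330 / 660 = 50%, so the share in 6.2 is the planned allocation in Protocol 10.3 and SAP 2.7 turned into a recommendation to each site.

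**Scale at a site.** With 660 patients over 30 to 40 dermatologists, the average is 660/40 = 16.5 to 660/30 = 22 patients per site. Half of that is 8.25 to 11 adalimumab starts, a count that a physician can easily follow.

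**The two readings.** Suppose a site's natural share among consecutive qualifying patients is not close to 50%.

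1. Prescribing reading. The site moves toward 50% by starting more or fewer patients on adalimumab. This conflicts with 6.1, 4.0 and 6.5, and with SAP 2.9.
2. Enrolment reading. Prescribing is untouched, and the site moves toward 50% by choosing which already-treated patients to enter. This satisfies the prescribing rule in 6.1, but conflicts with the consecutive assessment in 6.5.1 and the invitation of all who qualify in 6.1.

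The documents give no third route. Where the natural share is near 50%, nothing needs to move and the passages are compatible.

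**Timing.** Section 6.5.1 screens patients whose change is still under consideration, 6.1 puts the decision before screening, and 4.0 puts it before enrolment. Criterion iv keeps an undecided patient out of the cohort. It concerns the decision to change or add treatment, and does not say that the agent was chosen before screening or independently of the study.

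**What the share contributes to power.** Inputs from Protocol 10.3: response 50% (adalimumab), 40% (systemic), 32% (topical), two-sided 5%, 25% attrition. Assumptions: N fixed at 660, adalimumab share varied from 20% to 60%, the rest split equally between the comparators, whose combined rate is then (40% + 32%)/2 = 36%. Unadjusted comparison of two proportions:

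power = Φ{ [|p1 − p2| − 1.96·√(p̄(1 − p̄)(1/n1 + 1/n2))] / √(p1(1 − p1)/n1 + p2(1 − p2)/n2) }

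Example at the planned 330:165, 50% against 40%: p̄ = (165 + 66)/495 = 0.4667. The first root is 0.04757, and 1.96 times it is 0.0932. The second root is 0.04703. Power = Φ(0.0068/0.0470) = Φ(0.144) = 55.7%.

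Each cell gives power in % with all 660 evaluable / with 25% attrition:

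| Adalimumab share | Group sizes | 50% v 40% | 50% v 36% | 40% v 32% |
|---|---|---|---|---|
| 20% | 132:264:264 | 47.3 / 37.5 | 83.5 / 72.1 | 48.2 / 38.1 |
| 30% | 198:231:231 | 54.7 / 43.6 | 91.8 / 82.7 | 43.3 / 34.1 |
| 40% | 264:198:198 | 57.0 / 45.6 | 94.7 / 87.2 | 38.1 / 30.0 |
| 50% | 330:165:165 | 55.7 / 44.4 | 95.4 / 88.5 | 32.7 / 25.7 |
| 60% | 396:132:132 | 51.3 / 40.6 | 94.7 / 87.1 | 27.2 / 21.5 |

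Between 30% and 50%, the share hardly changes power for adalimumab against systemic agents. It helps adalimumab against both comparators combined, mainly by avoiding a low share. It reduces power for systemic against topical.

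**The case against.** The strongest reply is that 6.2 is a recommendation under a heading about enrolment numbers, while 6.1 is mandatory and is repeated elsewhere. A sensible site would let 6.1 govern and treat the 50% as a mix. Other text also limits any shift in prescribing: the sponsor neither supplies nor reimburses treatment (6.5.2), provincial criteria apply (6.1), and off-label patients are excluded (6.0). A common share across sites would, if met, even reduce confounding by site.

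Much of this stands, and it rules out four stronger conclusions that a reader might draw:

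- That the passages can never all be followed. They can where a site's natural mix is near 50%, and the mix reading is compatible with the prescribing rule in 6.1.
- That undecided patients will enter the cohort. Criterion iv excludes them, and the site audit covers that criterion.
- That the propensity score fails because it cannot explain a site's distance from 50%. A propensity score has to balance prognostic factors. Variation in assignment unrelated to prognosis does not confound, and the documents show no link between that distance and outcome.
- That the problem can be sized by assuming some fraction of the 330 adalimumab starts is shifted. The fraction would be arbitrary, and the result would be a count of patients, with no direction or effect on the estimate.

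The reply does not remove the conflict. The recommendation speaks of patients being started on treatment, where a mix would speak of patients being entered. The mix reading collides with consecutive assessment, and a site is not told which reading applies.

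**Conclusion.** The conflict is real and lies in the current text. Protocol 6.2 has the study recommend a site-level treatment share, while Protocol 4.0, 6.1 and 6.5 and SAP 2.9 keep the study out of the treatment decision. Either reading of 6.2 strains another section unless the site's natural mix is already near 50%.

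The documents do not show that prescribing or entry will in fact be influenced, and they give no basis for the size or direction of a bias. The weakness is that independence is asserted and cannot be checked from the data to be collected.

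The power figures rest on the plan's assumed response rates, an equal split of comparators and unadjusted comparisons. They show only that a site-level share is not needed to hold power over a plausible range of mixes. The plan's base figure of 360 does not reproduce from its own rates (50% v 40% at 180:180 has 48% power, 50% v 36% has 77%). That is a separate matter, and this conclusion does not depend on it.

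**What to change.** Reconcile the sections by wording alone, leaving prescribing untouched.

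1. Reword Protocol 6.2 so that 330:165:165 is a study-level enrolment expectation, and state that it guides neither prescribing nor selection at a site.
2. Align the screening wording in 6.5.1 with criterion iv in 6.1.1 and with the timing in 6.1, so that one point in time is used throughout.
3. Add to the CRF the date of the treatment decision and the agent chosen, so that independence can be checked.
4. Optionally, keep a screening log of consecutive eligible patients with their already-decided treatment, which would make any selective entry visible.

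Closing a full cohort centrally is not a clean alternative. Entry would still depend on treatment, and treatment could become tied to calendar time or site.

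The cost is a protocol wording change, a small amount of extra data entry, and an achieved mix that may differ from 2:1:1. On the assumptions in the table, a fall in the adalimumab share from 50% to 30% costs about 1 percentage point of power for adalimumab against systemic agents and about 4 against both comparators combined, with all 660 evaluable. A fall to 20% costs about 8 and 12.

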## 6.3 Investigator Selection Criteria

- i. A random sample of 30-40 dermatologists will participate in the study.
  - a. Physicians participating in the study must have experience in the conduct of clinical research and in particular good clinical practices (GCP) or must be willing to be trained in GCP.

## 6.4 Study Duration

All patients will be followed for 24 months. Given the observational nature of the study there will be no pre-defined protocol driven assessments and physician visits could take place according to the routine practice or the judgment of the treating physician. However, assessments at 3, 6, 12, 18 and 24 months after baseline will be recommended and encouraged given that this is within the acceptable practice patterns for patients undergoing treatment for moderate to severe psoriasis. In certain cases patients may be assessed more frequently than what will be recommended. Physicians will be asked to record in the Case Report Forms data from all visits occurring during the study period.

## 6.5 Study Conduct

The following sections describe the details regarding the execution of the study.

This is a multi-center Canadian observational study utilizing a prospective cohort design. As an observational study there will be no interventions or interference with the routine care of the patient.

All treatments will be prescribed and utilized as per the judgment of the treating physician and in accordance with the product monograph and regional requirements.

As per the product monograph: "Before initiation, during and after treatment with adalimumab patients should be evaluated for active or latent tuberculosis infection with a

tuberculin skin test. Treatment of latent tuberculosis infections should be initiated prior to therapy with adalimumab. When tuberculin skin testing is performed for latent tuberculosis infection, an induration size of 5 mm or greater should be considered positive, even if vaccinated previously with Bacille Calmette-Guérin (BCG). The possibility of undetected latent tuberculosis should be considered especially in patients who have immigrated from or traveled to countries with a high prevalence of tuberculosis or who had close contact with a person with active tuberculosis. If latent infection is diagnosed, appropriate prophylaxis in accordance with the Canadian Tuberculosis Standards and Centers for Disease Control and Prevention guidelines should be instituted. Anti-tuberculosis therapy prior to initiating HUMIRA® should also be considered in patients who have a negative test for latent tuberculosis but have risk factors for tuberculosis infection. The decision to initiate antituberculosis therapy in these patients should only be made after taking into account both the risk for latent tuberculosis infection and the risks of anti-tuberculosis therapy. If necessary, consultation should occur with a physician with expertise in the treatment of tuberculosis. Active tuberculosis has developed in patients receiving adalimumab whose screening for latent tuberculosis infection was negative, and some patients who have previously received treatment for latent or active tuberculosis have developed active tuberculosis while being treated with TNF-blocking agents. Patients receiving adalimumab should be monitored for signs and symptoms of active tuberculosis, particularly because tests for latent tuberculosis infection may be falsely negative. The risk of false negative tuberculin skin test results should be considered especially in patients who are severely ill or immunocompromised. Patients should be instructed to seek medical advice if signs/symptoms (e.g., persistent cough, wasting/weight loss, low grade fever) suggestive of a tuberculosis infection occur, and physicians should monitor for signs and symptoms of active tuberculosis, including patients who are tuberculosis skin test negative" (HUMIRA® Product Monograph).

With respect to the frequency and schedule of assessments, although there are no study specific requirements, follow up visits at 3, 6, 12, 18 and 24 months after baseline will be

recommended. Data obtained from more frequent visits or visits conducted at other time points will also be recorded in the study Case report Form. In fact, in order to avoid any bias and loss of information all information regarding the management of the patients during the 24 month follow up period of the study should be recorded in the study data collection forms. In addition to clinical data that will be ascertained by the treating physician, patient reported outcomes will also be ascertained through self administered questionnaires.

The following table describes the data that will be collected and the recommended timing of the assessments.

**Table 1: Study Data Variables Collected by Visit** 

|                                                           | 3.4   |    |    |    |    |    |
|-----------------------------------------------------------|-------|----|----|----|----|----|
| 1                                                         | Month |    |    |    |    |    |
| Variable                                                  | 0     | 3  | 6  | 12 | 18 | 24 |
| Visit Number                                              | 1     | 2  | 3  | 4  | 5  | 6  |
| Demographics:                                             |       |    |    |    |    |    |
| Age                                                       | X     |    |    |    |    |    |
| Gender                                                    | X     |    |    |    |    |    |
| Employment status                                         | X     |    |    |    |    |    |
| Smoking                                                   | X     |    |    |    |    |    |
| Alcohol use                                               | X     |    |    |    |    |    |
| Anthropometric measurements:                              |       |    |    |    |    |    |
| Height                                                    | X     |    |    |    |    |    |
| Weight                                                    | X     | X  | X  | X  | X  | X  |
| Physical Examination                                      | X     | X1 | X1 | X1 | X1 | X1 |
| Medical History:                                          |       |    |    |    |    |    |
| Previous Conditions                                       | X     | X1 | X1 | X1 | X1 | X1 |
| Current Comorbidity                                       | Λ     | AI | Λ1 | AI | AI | AI |
| Family History                                            |       |    |    |    |    |    |
| Psoriasis History                                         |       |    |    |    |    |    |
| Date of diagnosis                                         | X     |    |    |    |    |    |
| Known triggers                                            | X     |    |    |    |    |    |
| Frequency and Pattern of Flare – Ups                      | X     |    |    |    |    |    |
| Family History of Psoriasis                               | X     |    |    |    |    |    |
| Prior Treatment Details:                                  |       |    |    |    |    |    |
| Dose                                                      | X     |    |    |    |    |    |
| Duration                                                  |       |    |    |    |    |    |
| Reason for discontinuation                                |       |    |    |    |    |    |
| Concomitant Medications (Emphasis on Psoriasis Treatment) | X     | X  | X  | X  | X  | X  |
| Concomitant Psoriatic Arthritis                           | X2    |    |    |    |    |    |
| Rheumatoid Factor                                         | X2    |    |    |    |    |    |
| C - Reactive Protein or hs- CRP                    | X2    | X2 | X2 | X2 | X2 | X2 |
| Erythrocyte Sedimentation Rate (ESR)                      | X2    | X2 | X2 | X2 | X2 | X2 |
| Clinical Laboratory Tests                                 | X2    | X2 | X2 | X2 | X2 | X2 |

|                                                                    | Month |    |    |    |    |    |
|--------------------------------------------------------------------|-------|----|----|----|----|----|
| Variable                                                           | 0     | 3  | 6  | 12 | 18 | 24 |
| Visit Number                                                       | 1     | 2  | 3  | 4  | 5  | 6  |
| Body Surface Area (BSA)                                            | X     |    | X  | X  | X  | X  |
| Psoriasis and Arthritis Screening Questionnaire (PASQ)             | X     | X  | X  | X  | X  | X  |
| Use of Phototherapy                                                | X     | X  | X  | X  | X  | X  |
| Physician's Global Assessment of Disease Activity (6 Point Likert) | X     | X  | X  | X  | X  | X  |
| Patient's Global Assessment of Disease Activity (VAS)              | X3    | X3 | X3 | X3 | X3 | X3 |
| Dermatology Life Quality Index                                     | X3    | X3 | X3 | X3 | X3 | X3 |
| Medical Outcomes Study – Short Form 12                             | X3    |    | X3 | X3 |    | X3 |
| Health Care Utilization Questionnaire                              | X3    |    | X3 | X3 |    | X3 |
| Beck Depression Inventory                                          | X3    |    | X3 | X3 |    | X3 |
| Work Limitations Questionnaire                                     |       |    | X3 | X3 |    | X3 |
| Rheumatology Consult4                                              | X     | X  | X  | X  | X  | X  |
| Compliance assessment                                              |       | X  | X  | X  | X  | X  |

- 1. Only changes from previous visit will be recorded
- 2. Only if used as part of routine care. For the baseline visit, historical data up to 6 months could be used.
- 3. Self Administered questionnaires. These could be completed at the physician's office, at home and sent by mail.
- 4. Relevant sections of the Case Report Form to be completed by rheumatologists or information must be obtained from the rheumatologists.

